
Objectives

The primary objective is to test the feasibility of treating chronic pain with yoga delivered via telehealth. We will modify an existing yoga intervention for chronic musculoskeletal pain and address the technical challenges of at-home teleyoga. Then, using the modified intervention, we will demonstrate the feasibility of conducting a randomized controlled trial involving at-home teleyoga.

Specific Aims and Hypothesis

Specific Aims:

1. Modify an existing yoga intervention for chronic musculoskeletal pain and address the technical challenges of at-home teleyoga.
2. Demonstrate the feasibility of conducting a randomized controlled trial involving at-home teleyoga.

Hypothesis 1 (primary): a) Treatment satisfaction as measured by the Multi-Dimensional Treatment Satisfaction Measure will be neutral or positive for all factors. B) Treatment satisfaction will be at least neutral for all items.

Hypothesis 2 (secondary): a) It will be feasible to recruit 30 participants over a 3-month period and deliver yoga in-person or via at-home teleyoga while maintaining a retention rate commensurate with other similar studies. b) Fidelity of treatment delivery will be acceptable as measured by scoring of taped sessions. c) We expect participants will complete the PROMIS measures with a missing data rate not to exceed 15% per participant. d) The yoga intervention will be safe with no serious adverse events in either treatment group.

Study Design

This study aims to investigate the feasibility of at-home teleyoga for veterans with chronic musculoskeletal pain. We will demonstrate the feasibility of conducting a randomized controlled trial involving at-home teleyoga. We will randomize veterans (N=30) with chronic musculoskeletal pain to at-home teleyoga or in-person yoga. Primary feasibility outcomes will include recruitment rates, retention, protocol adherence, participant satisfaction from semi-structured questionnaires, adverse events, treatment fidelity, and rates of completion of study instruments. Feasibility will be determined by comparison to benchmarks from studies that used similar interventions and populations.

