We intend to recruit local (residing in the San Francisco Bay Area), outpatient adult veterans with chronic musculoskeletal pain to enroll in this clinical trial. This research proposal will use randomization after baseline assessments to assign participants (n=30) to at-home teleyoga or in-person yoga (n=15 per group). Randomization will occur by identifying group membership in 30 sealed envelopes and having each participant draw one envelope. To be representative of the veteran population at VAPAHCS Health Care System (VAPAHCS) each group will have 1-2 females.

All human subjects research will be performed at VAPAHCS in Palo Alto, California or at the homes of the veterans (residing in the San Francisco Bay Area) who receive the at-home teleyoga group. There are no other collaborating sites where human subjects research will be performed.

Month					
1	2	3	4	5	6
Recruit (n=30)			Run in-person yoga groups (n=15) Run at-home teleyoga groups (n=15)		

Table 1. Recruitment Table

Group assignment and randomization

Eligible participants will be added to a cohort list; when 30 have been identified, the study team will schedule baseline assessments. After the baseline assessments, participants will be randomized to in-person or at-home teleyoga (n=15 per group). Randomization will occur by identifying group membership in 30 sealed envelopes and having each participant draw one envelope. Each group will contain 1-2 females, to be representative of the veteran population at VAPAHCS.

Statistical Plan and Data Analysis

Fidelity and Missing Data Benchmarks

Fidelity: The instructors will review the video recorded sessions using a manual checklist for instructor adherence to the yoga manuals, which will consist of a Yes/No for each procedure or instruction.

Missing Data: Like similar behavioral outcome measures, we expect missing data in the PROMIS-PI measures not to exceed 15%.

The main analytic strategy will be descriptive statistics at pre- and post-intervention assessments in each arm. We will then preliminarily compare the two conditions in line with the intention to treat principle. The purpose of these comparisons is not to provide formal inference but provide preliminary information to guide the adequately powered future trial.

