Treatment Satisfaction: Assessed using the Multi-Dimensional Treatment Satisfaction Measure (MDTSM). The measure consists of 11 subscales assessing treatment process and outcome attributes. Each subscale has 1-8 items (see Table 5). Each question except the Discomfort subscale is rated on a five-point scale ranging from “not at all (0)” to “very much (4)”. Thus, a score of 2 represents a rating of neutral satisfaction. The instrument was developed for behavioral interventions and is designed to provide a comprehensive set of treatment attributes to consider when evaluating treatments in the context of pilot studies. It is designed to be completed after exposure to an intervention, to point to aspects of treatments that are viewed favorably or unfavorably. The MDTSM is relevant to many types of behavioral interventions and can be tailored to our yoga intervention. The MDTSM subscales demonstrates good internal consistency, reliability, and validity.

	Data Collection			
	Screening	Baseline	Yoga (wks 1-12)	Post-treatment
Background				
Consent Form	×			
Demographic Questionnaire	×			
Clinical Questionnaire	×			
Yoga Medical Clearance Form	×			
Medical Use		×		×
Yoga Home Practice Log			×	
Mental Health				
BDI-II		×		×
Pain/QOL/Physical				
BPI-SF		×		×
DVPRS	×			
PEG	×	×		×
PROMIS-PI		×		×
Behavioral				

Treatment Satisfaction				x
Provider Suggestions				x
Patient Safety			x	x
Treatment Fidelity			x	

Table 2. Study Measures and Timetable of Data Collection

Yoga Treatment

Participants will be randomized to in-person yoga (n=15) or online yoga (n=15). Yoga classes will be 75-minutes and will be delivered by a yoga instructor once a week over a course of 12 weeks in-person or online.

Yoga (in-person): Veterans in the in-person yoga group will attend yoga classes at VAPAHCS. The yoga instructor will provide weekly instruction at the VAPAHCS in a telehealth-equipped conference room.

Yoga (online): The yoga instructor will provide weekly instruction using approved teleconferencing software either from an offsite location or from the VAPAHCS in a telehealth-equipped conference room.

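### Does the missing neutral point for the Discomfort subscale leave the primary satisfaction hypothesis impossible to judge?

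*Combined protocol and SAP*

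**What the plan says.** Under Specific Aims and Hypothesis, Hypothesis 1 is labelled primary and has two parts: "Treatment satisfaction as measured by the Multi-Dimensional Treatment Satisfaction Measure will be neutral or positive for all factors" and "Treatment satisfaction will be at least neutral for all items".

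Under Study Assessments, the Treatment Satisfaction entry describes the instrument: "The measure consists of 11 subscales assessing treatment process and outcome attributes". Subscales have between 1 and 8 items, and the reader is sent to a Table 5 for them. On response format it says "Each question except the Discomfort subscale is rated on a five-point scale ranging from" 0 (not at all) to 4 (very much). It then concludes: "Thus, a score of 2 represents a rating of neutral satisfaction".

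The Statistical Plan and Data Analysis section gives no scoring or decision rule for the MDTSM. Its general approach is: "The main analytic strategy will be descriptive statistics at pre- and post-intervention assessments in each arm". Of the comparisons between arms it adds: "The purpose of these comparisons is not to provide formal inference but provide preliminary information to guide the adequately powered future trial".

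**The concern.** Both parts of Hypothesis 1 are conjunctions: one factor or item below neutral defeats the hypothesis, and one that cannot be judged prevents it from being confirmed. The only neutral value in the document is derived from a scale that Discomfort is expressly said not to use. Read literally, one required component of the primary criterion has no threshold.

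There is also a question of direction. If Discomfort is scored so that higher is worse, and an analyst carries the cut of 2 across by habit, a comfortable intervention fails and an uncomfortable one passes. For a physical intervention in people with chronic pain, discomfort is not a dimension to get backwards. If the choice were left until the data had been seen, it could also be made to suit the result.

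**Working it through.** **Inputs.** From the Treatment Satisfaction entry: 11 subscales, a 0-4 rating for all but Discomfort, and neutral = 2. From Specific Aims and Hypothesis: every factor and every item must be at least neutral. The document gives no range, anchors or direction for Discomfort, so any figure for it below is an assumption.

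**Step 1: reproduce the neutral value.** Midpoint = (minimum + maximum)/2 = (0 + 4)/2 = 2. This agrees with the plan.

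**Step 2: coverage.** 11 − 1 = 10 subscales have a defined neutral point. One of 11 (9%) does not.

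**Step 3: what a misapplied cut would do.** Assume that higher means more discomfort. For a range lo to hi, take a low-discomfort mean at lo + 0.15 × (hi − lo) and a high-discomfort mean at lo + 0.85 × (hi − lo). Judge each first by a raw cut of 2, then after reversing (lo + hi − score) against the scale's own midpoint.

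| Assumed range | Midpoint | Low mean | Raw cut of 2 | Reversed, own midpoint | High mean | Raw cut of 2 | Reversed, own midpoint |
|---|---|---|---|---|---|---|---|
| 0-4 | 2 | 0.6 | fails | 3.4, passes | 3.4 | passes | 0.6, fails |
| 1-5 | 3 | 1.6 | fails | 4.4, passes | 4.4 | passes | 1.6, fails |
| 0-10 | 5 | 1.5 | fails | 8.5, passes | 8.5 | passes | 1.5, fails |
| 0-3 | 1.5 | 0.45 | fails | 2.55, passes | 2.55 | passes | 0.45, fails |
| 0-1 | 0.5 | 0.15 | fails | 0.85, passes | 0.85 | fails | 0.15, fails |

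The raw cut gives a reversed verdict on four of the five assumed ranges, and on 0-1 it can never be met. Reversed and judged at its own midpoint, Discomfort behaves properly on all five. So the harm comes from carrying the cut across, not from including the subscale.

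**Step 4: does the plan carry the cut across?** The exception for Discomfort stands in the sentence about the 0-4 scale, and the value 2 is stated in the next sentence as a consequence of that scale. An analyst who follows the text has no instruction to use 2 for Discomfort. Hypothesis 1 itself is worded in terms of satisfaction being neutral or positive, not as a numerical score, and on that wording less discomfort is the favourable direction.

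**Step 5: when does the gap affect the verdict?**
- If any of the other 10 subscales, or any of their items, falls below 2, Hypothesis 1 fails whatever Discomfort shows.
- If all 10 and all their items reach 2, the verdict depends on how Discomfort is scored.

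Only the second case, a confirmed pass, needs the missing definition.

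**The case for a change.** The strongest case for a change is that this is the trial's only hypothesis labelled primary, and a descriptive threshold needs a value and a direction just as a test does. The statement that formal inference is not intended concerns comparisons between the arms, so it does not excuse an incomplete criterion for satisfaction. Reversing the score would not by itself supply a neutral point on an unstated scale. Even if Table 5 gives the response format, the plan would still have to say which point on it counts as neutral. A sentence or two would settle the matter at no cost in patients or data.

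Much of that stands. The supplied text does not define neutral for Discomfort, and a clean pass cannot be confirmed from it alone. What does not stand is the step from there to an error in the plan. Table 5 is cited for the subscales and their items but is not in the supplied text, so whether the response format was ever given is unknown. Nor does any stated go/no-go decision rest on Hypothesis 1: Study Design lists seven primary feasibility outcomes, of which satisfaction is one, and judges feasibility against benchmarks from similar studies. The plan describes the MDTSM as a means of showing which aspects of a treatment are liked or disliked, and reporting each subscale does that with or without a pass label.

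The obvious edit also gains little. Limiting the rule to the 10 subscales rated 0-4 and reporting Discomfort separately against its own cut still leaves that cut to be chosen. It would also take out of the primary hypothesis the one subscale named for unpleasant effects, which makes the hypothesis easier to meet.

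**Conclusion.** No change to the plan follows. The gap is real but narrow: one of 11 subscales has no stated neutral point, and this matters only if the other 10 subscales and all their items reach 2. The reversed verdict is not the plan as written; it needs an analyst to apply a cut that the plan reserves for another scale, and a scoring direction that the plan does not state. What is left is a scoring detail that the analysts of a mainly descriptive pilot with 15 participants per arm can be expected to fill sensibly, by reading Discomfort on its own scale with less discomfort as the favourable direction.

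This rests on three assumptions: that the Discomfort items have a response format known to the study team, whether from Table 5 or from the questionnaire; that the format is read in its natural direction; and that Hypothesis 1 is used to describe acceptability and not as the sole gate to a later trial. The documents contradict none of these, but they do not confirm the first two.
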